17.5 Process for informing Study Team

Regular team meetings will be conducted where study procedures, questions and issues will be discussed and resolved.

18.0 Other Approvals

The FDA will require submission of an IND (Investigational New Drug) application.

The Institutional Biosafety Committee Review and Registration

19.0 Subject Stipend (Compensation) and/or Travel Reimbursements

Part 1: Subjects will be compensated \$20 for attending the study visit regardless of whether or not they are eligible to continue after in-person screening. Subjects will receive an additional \$100 for completing the study. Participants have the option of being provided lunch from our cafeteria if their appointment falls during this time.

Part 2: Subjects will be compensated \$20 for attending the study visit regardless of whether or not they are eligible to continue after in-person screening. Subjects will receive an additional \$220 for completing the study. Participants have the option of being provided lunch and dinner from our cafeteria.

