3.3 Early Withdrawal of Subjects

3.3.1 Criteria for removal from study

Participation may be discontinued if the principal investigator (PI) determines it is the best decision in order to protect the safety of a participant. The participant may be removed from the research study without his or her permission because the participant does not follow the instructions for the study, has an adverse reaction to the study product (irregular heartbeat, palpitations, tachycardia (resting heart rate persistently greater than 100 beats per minute), has symptoms of nicotine overdose such as nausea, vomiting, dizziness, weakness, or rapid heartbeat, or has symptoms of an allergic reaction.

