5.1.1.2 Coercion or Undue Influence during Consent

Recruitment materials for the study will be broadly distributed throughout the community. Once participants contact the study center, they will be given information about the study and offered the opportunity to participate. The researchers obtaining consent will be instructed to clearly indicate that the participant's enrolling in the trial is purely voluntary and the researchers will not offer comments about whether they believe the participant should enroll in the study or not. Compensation provided to the participant for the study is modest.

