Participants will receive one film at this visit after completing baseline measures (approximately 8 AM). They will be instructed to allow the film to dissolve in their mouth without chewing or swallowing it and to report to the researcher when he or she feels that the film has completely dissolved. Four participants each will receive a randomly allocated dose of either (a) 0mg, (b) 2mg or (c) 4mg oral nicotine film. The Time and Events table above details the order of events and timing for biomeasures, questionnaires and 11 total blood draws. However, if the film dissolves within one minute of a set blood draw time, the blood draw that is to be completed one minute after the film dissolves will be omitted.

Payment:

Participants will receive \$120 for completing this visit.

Part 2- Screening (Phone)

Participants will be instructed to drink water prior to their visit to help the blood draw process go smoothly. They will also be instructed that they may choose to have meals from our cafeteria but may also bring snacks if they would like. Participants will also be informed that they can bring personal items such as laptops, books, etc. for use during their visit.

Part 2- Screening (In Person)

Participants will be re-screened for eligibility and informed consent for the appropriate part of the study will be obtained by research staff.

After consent, additional eligibility screening materials will include:

1. A review of medications and medical history
2. NIDA Drug Screener
3. Blood Pressure (systolic must be \leq 140 mm Hg, diastolic must be \leq 90 mm Hg)
4. Urine pregnancy test (if applicable)
5. Exhaled Carbon Monoxide <12 ppm

Part 2 Visit- 12 hours

Clinical measures and questionnaires will be conducted as outlined in the table below.

An IV will be inserted for access for 20 blood draws in Part 2. Time and contents of participant meals/snacks will also be recorded so as to enable researchers to assess food intake and timing as it relates to timing of nicotine absorption from the film.

Part 2: Time and Events Table														
	Screening		Part 2 Procedures											
Study Hour	-2	-1	0	1	2	3	4	5	6	7	8	9	10	11
Administer Film			X			X			X			X		
Blood Draws														
Baseline Blood		X												
Hour 0 Blood			Min 30, 45											
Hour 1 Blood				Min 0										
Hour 2 Blood					Min 0									
Hour 3 Blood						Set Mins: 0, 30, 45								
Hour 4 Blood							Min 0							
Hour 5 Blood								Min 0						

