Hour 6 Blood									Set Mins: 0,30,45					
Hour 7 Blood										Min 0				
Hour 8 Blood											Min 0			
Hour 9 Blood												Set Mins: 0, 30,45		
Hour 10 Blood													Min 0	
Hour 11 Blood														Min 0
Study Hour	-2	-1	0	1	2	3	4	5	6	7	8	9	10	11
Measures														
Screener 2	X													
Concomitant Medications	X													
Medical History	X													
NIDA	X													
CES-D	X													
Oropharyngeal Exam		X												X
Blood Pressure & Heart Rate	X	X	Min 30	Min 0, 30	Min 0, 30	Min 0, 30	Min 0, 30	Min 0, 30	Min 0, 30	Min 0, 30	Min 0, 30	Min 0, 30	Min 0, 30	Min 0
CO Reading	X													
Pregnancy Test	X													
Anthropometrics	X													
Demographics	X													
Dependence	X													
Cigarette Details	X													
Tobacco Use History		X												
Minnesota Withdrawal Scale		X	Min 50	Min 50		Min 50	Min 50		Min 50	Min 50		Min 50		Min 50

Questionnaire of Smoking Urges		X	Min 50	Min 50		Min 50	Min 50		Min 50	Min 50		Min 50	Min 50
Study Product Side Effects			Min 50	Min 50		Min 50	Min 50		Min 50	Min 50		Min 50	Min 50
Study Product Evaluation						Min 0							X
Likelihood of Use Scale						Min 0							X
Dose Awareness													X
Payment													\$240

Film Administration, Dosing and Blood draws:

Participants will receive four doses of nicotine film during this visit. Four participants each will be randomly allocated to consume four films over twelve hours in the following orders (a) 0,0,0,0mg (b) 2,2,2,2, or (c) 4,4,0,4. The first film will be administered upon completion of baseline measures (approximately 8AM). Again, participants will be instructed to allow the film to dissolve in their mouth, without chewing or swallowing it and to report to the researcher when he or she feels that the film has completely dissolved. Films will be administered every three hours (approximately 11 AM, 2 PM, and 5 PM). The Time and Events table above details the order of events and timing for biomeasures, questionnaires and 20 total blood draws.

Payment:

Participants will receive \$240 for completing this visit.

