11.2 Data that are reviewed

Data that will be reviewed include:

- Accrual and retention
- Adverse events and serious adverse events
- Protocol deviations/violations
- Changes in subjective effects (particularly dizziness and nausea, the most common nicotine effects)
- Changes in heart rate and blood pressure
- Oropharyngeal changes

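### Most of the visit payment depends on completion, while self-reported nausea or dizziness can lead to removal at the investigator's discretion, so participants have a financial reason to under-report part of the secondary endpoint

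*Combined protocol and SAP*

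**What the plan says.** **Payment.** For each part, section 19.0 gives "20 for attending the study visit regardless of whether or not they are eligible to continue after in-person screening" (dollars). The balance is "100 for completing the study" in Part 1 and "220 for completing the study" in Part 2. The two Payment paragraphs in section 7.2 state the totals with the same condition: "120 for completing this visit" and "240 for completing this visit". None of these places says what is paid to someone who is removed or who leaves part-way.

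**Removal.** Section 3.3.1, repeated in section 12.0, permits removal without the participant's agreement on several grounds. One is that the participant "has symptoms of nicotine overdose such as nausea, vomiting, dizziness, weakness, or rapid heartbeat". The wording is permissive and gives no severity threshold for nausea or dizziness.

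**Use of the symptom data.** Section 1.3 makes subjective ratings of the film and side effects the secondary endpoint. Section 12.0 says side effects are collected by participant questionnaire after each film. Section 11.2 lists for safety review "Changes in subjective effects (particularly dizziness and nausea, the most common nicotine effects". Sections 7.4.2 and 11.6 have Part 1 reactions and data reviewed before Part 2 opens, with possible changes to the planned doses.

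**Amount.** On undue influence at consent, section 5.1.1.2 says "Compensation provided to the participant for the study is modest".

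**The concern.** Nausea and dizziness have no objective measure in this study: they are known only if the participant reports them. A participant who has read the payment terms and the removal terms can see that reporting them might end the visit and most of the payment with it. The incentive runs towards silence on the symptoms the study most needs to hear about.

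It is also unlikely to be equal across arms. The withdrawal symptoms that section 12.0 expects, and expects to be worse on placebo, are irritability, restlessness, poor concentration and anxiety. These are not on the removal list; the symptoms of nicotine excess are. Under-reporting would therefore fall mainly on the 2 mg and 4 mg groups and would favour the prediction in section 1.1 that the film is safe and well tolerated.

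Two further uses are exposed. The review between parts would see fewer reactions than occurred. Within a Part 2 visit, a reaction concealed after one film would not be known when the next was given.

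**Working it through.** **Step 1. Reproduce the plan's totals.** Total = attendance payment + completion payment (section 19.0), compared with section 7.2.

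| | Attendance | Completion | Sum | Section 7.2 total |
|---|---|---|---|---|
| Part 1 | $20 | $100 | $120 | $120 |
| Part 2 | $20 | $220 | $240 | $240 |

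The two sections agree.

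**Step 2. Share at risk.** Share = completion payment / total.

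- Part 1: 100/120 = 83.3% at risk; 20/120 = 16.7% kept.
- Part 2: 220/240 = 91.7% at risk; 20/240 = 8.3% kept.

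This assumes that a removed participant receives the attendance payment and nothing more, which is the plain reading of a completion condition with no pro-rating stated.

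**Step 3. Match symptoms to roles.**

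| Symptom | Removal ground (3.3.1, 12.0) | Called most common (11.2) | Known only by self-report |
|---|---|---|---|
| Nausea | Yes | Yes | Yes |
| Dizziness | Yes | Yes | Yes |
| Weakness | Yes | No | Largely |
| Vomiting | Yes | No | No; hard to hide on site |
| Rapid heartbeat | Yes | No | No; heart rate is measured on schedule |

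The concern is strongest for nausea and dizziness. They are only part of the side-effect data: section 12.0 also mentions mouth discomfort or irritation, diarrhea and hiccups, and the questionnaire items are not listed.

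**Step 4. How much one concealed report matters.** Section 7.2 allocates four participants to each arm in each part. One concealed reaction is 1/4 = 25% of an arm. Section 16.0 continues screening until twelve have completed each part, and section 3.3.2 gives follow-up of withdrawn participants as not applicable. Those removed are therefore replaced by completers, which could tilt the data the same way.

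**Step 5. Illustration only.** The documents give neither a symptom rate nor a concealment rate. Assume that 30% of the 8 actively dosed participants in a part (4 + 4) have nausea or dizziness, independently, with the two active doses pooled. With a fraction c concealing, P(no report) = (1 − 0.30 × (1 − c))^8.

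- c = 0: 0.70^8 = 0.058
- c = 0.5: 0.85^8 = 0.272
- c = 1: 1.00^8 = 1

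Concealment could thus leave the chance of a clean-looking part at 5.8% or raise it anywhere up to certainty. The documents do not say where in that range the study would fall, so this shows direction and not an estimate.

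**The case against.** The strongest reply is that reporting a symptom does not trigger removal. Section 3.3.1 is discretionary and describes the listed symptoms as signs of nicotine overdose; section 12.0 calls nausea, dizziness and rapid heartbeat mild. The schedule repeats the side-effect questionnaire through both visits, so people with symptoms are evidently expected to carry on. This stands against any claim that honest reporting automatically costs the payment. It does not remove the incentive, because participants cannot know beforehand how the discretion will be used.

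Part 1 is weaker ground than Part 2. It gives a single film, so there is no later dose to withhold, and removal would mainly cut sampling short. The 83% is correct arithmetic for an outcome that may be rare.

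Self-report is not the only safety channel. Heart rate and blood pressure are taken about every half hour, a nurse examines the mouth before and after product use, participants stay on site under supervision, and the review between parts covers all Part 1 data including blood nicotine. A reader might infer that self-report is the main safety input; the documents do not say so. Nor can under-reporting alter the plasma nicotine values that form the primary endpoint.

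The consent pages are not in the review file and may contain a pro-rating clause. That stands as a limit: the statement that removed participants are not paid holds only for the protocol text that can be seen. If such a clause exists, sections 19.0 and 7.2 should agree with it.

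The description of compensation as modest concerns pressure to enrol. It does not change the share forfeited once a visit has begun.

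**Conclusion.** The concern holds as a poor incentive written into the payment rule. Completion-dependent pay is 83% of the Part 1 total and 92% of the Part 2 total. Symptoms that may lead to removal include two that are self-reported, part of the secondary endpoint and used in the review between parts. Any resulting bias would favour the film. Its size is unknown and could be zero.

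Three stronger readings are tempting and are not supported. First, that nausea, dizziness and rapid heartbeat together constitute the side-effect endpoint: they are some of its content, and rapid heartbeat is also covered by measurement. Second, that section 11.2 calls all the removal symptoms the most common nicotine effects: it says so only of dizziness and nausea. Third, that bias in the tolerability result has been shown: the documents support an incentive and its direction, not any amount of concealment.

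The conclusion assumes that completion means finishing the visit, that no pro-rating is set out in the missing consent pages, and that participants know both the payment and the removal terms. The change is worth making before enrolment; the primary endpoint is not at issue.

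**What to change.** In section 19.0 and in both Payment paragraphs of section 7.2, state that:

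1. a participant removed by the investigator for a symptom or reaction receives the full visit payment;
2. any other participant who leaves early is paid in proportion to time on site;
3. participants are told at consent that reporting symptoms does not reduce their pay.

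Make both consent forms agree. Full pay should be tied to the investigator's decision to remove and should not extend to anyone who chooses to stop and cites a symptom. The wider rule would let a Part 2 participant report nausea after the first film and leave with $240, which could reverse the incentive and inflate side-effect reports in every arm.

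The cost is protocol and consent wording, plus at most $100 (Part 1) or $220 (Part 2) per removed person; two Part 2 removals would cost up to 2 × $220 = $440. The incentive to finish is slightly weaker. No removal or dosing rule changes.

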20.0 Multi-Site Research

N/A

20.1 Communication Plans

N/A

20.2 Data Submission and Security Plan

N/A

20.3 Subject Enrollment

N/A

20.4 Reporting of Adverse Events and New Information

N/A

20.5 Audit and Monitoring Plans

N/A

21.0 Adverse Event Reporting

21.1 Adverse Event Definitions

For drug studies, incorporate the following definitions into the below responses, as written:	
Adverse event	Any untoward medical occurrence associated with the use of the drug in humans, whether or not considered drug related
Adverse reaction	Any adverse event caused by a drug
Suspected adverse reaction	Any adverse event for which there is a reasonable possibility that the drug caused the adverse event. Suspected adverse reaction implies a lesser degree of certainty about causality than "adverse reaction". 
• Reasonable possibility. For the purpose of IND safety reporting, "reasonable possibility" means there is evidence to suggest a causal relationship between the drug and the adverse event.
Serious adverse event or Serious suspected adverse reaction	Serious adverse event or Serious suspected adverse reaction: An adverse event or suspected adverse reaction that in the view of either the investigator or sponsor, it results in any of the following outcomes: Death, a life-threatening adverse event, inpatient hospitalization or prolongation of existing hospitalization, a persistent or significant incapacity or substantial disruption of the ability to conduct normal life functions, or a congenital anomaly/birth defect. Important medical events that may not result in death, be life-threatening, or require hospitalization may be considered serious when, based upon appropriate medical judgment, they may jeopardize the patient or subject and may require medical or surgical intervention to prevent one of the outcomes listed in this definition.
Life-threatening adverse event or life-threatening suspected adverse reaction	An adverse event or suspected adverse reaction is considered "life-threatening" if, in the view of either the Investigator (i.e., the study site principal investigator) or Sponsor, its occurrence places the patient or research subject at immediate risk of death. It does not include an adverse event or suspected adverse reaction that had it occurred in a more severe form, might have caused death.
Unexpected adverse event or Unexpected suspected adverse reaction.	An adverse event or suspected adverse reaction is considered "unexpected" if it is not listed in the investigator brochure, general investigational plan, clinical protocol, or elsewhere in the current IND application; or is not listed at the specificity or severity that has been previously observed and/or specified.

21.2 Recording of Adverse Events

All adverse events (serious or non-serious) and abnormal test findings observed or reported to study team believed to be associated with the study drug(s) or device(s) will be followed until the event (or its sequelae) or the abnormal test finding resolves or stabilizes at a level acceptable to the investigator.

An abnormal test finding will be classified as an adverse event if one or more of the following criteria are met:

- The test finding is accompanied by clinical symptoms

- The test finding necessitates additional diagnostic evaluation(s) or medical/surgical intervention; including significant additional concomitant drug treatment or other therapy
- The test finding leads to a change in study drug dosing or discontinuation of subject participation in the clinical research study
- The test finding is considered an adverse event by the investigator.

21.3 Causality and Severity Assessments

The investigator will promptly review documented adverse events and abnormal test findings to determine 1) if the abnormal test finding should be classified as an adverse event; 2) if there is a reasonable possibility that the adverse event was caused by the study drug(s) or device(s); and 3) if the adverse event meets the criteria for a serious adverse event.

If the investigator's final determination of causality is "unknown and of questionable relationship to the study drug(s) or device(s)", the adverse event will be classified as associated with the use of the study drug(s) or device(s) for reporting purposes. If the investigator's final determination of causality is "unknown but not related to the study drug(s) or device(s)", this determination and the rationale for the determination will be documented in the respective subject's case history.

21.4 Reporting of Adverse Reactions and Unanticipated Problems to the FDA

21.4.1 Written IND Safety Reports

The Sponsor-Investigator will submit a written IND Safety Report (i.e., completed FDA Form 3500A) to the responsible new drug review division of the FDA for any observed or volunteered adverse event that is determined to be a serious and unexpected, suspected adverse reaction. Each IND Safety Report will be prominently labeled, "IND Safety Report", and a copy will be provided to all participating investigators (if applicable) and sub-investigators.

Written IND Safety Reports will be submitted to the FDA as soon as possible and, in no event, later than 15 calendar days following the Sponsor-Investigator's receipt of the respective adverse event information and determination that it meets the respective criteria for reporting.

For each written IND Safety Report, the Sponsor-Investigator will identify all previously submitted IND Safety Reports that addressed a similar suspected adverse reaction experience and will provide an analysis of the significance of newly reported, suspected adverse reaction in light of the previous, similar report(s) or any other relevant information.

Relevant follow-up information to an IND Safety Report will be submitted to the applicable review division of the FDA as soon as the information is available and will be identified as such (i.e., "Follow-up IND Safety Report").

If the results of the Sponsor-Investigator's follow-up investigation show that an adverse event that was initially determined to not require a written IND Safety Report does, in fact, meet the requirements for reporting; the Sponsor-Investigator will submit a written IND Safety Report as soon as possible, but in no event later than 15 calendar days, after the determination was made.

21.4.2 Telephoned IND Safety Reports – Fatal or Life-threatening Suspected Adverse Reactions

In addition to the subsequent submission of a written IND Safety Report (i.e., completed FDA Form 3500A), the Sponsor-Investigator will notify the responsible review division of the FDA by telephone or facsimile transmission of any unexpected, fatal or life-threatening suspected adverse reaction.

The telephone or facsimile transmission of applicable IND Safety Reports will be made as soon as possible but in no event later than 7 calendar days after the Sponsor-Investigator's receipt of the respective adverse event information and determination that it meets the respective criteria for reporting.

21.5 Reporting Adverse Reactions and Unanticipated Problems to the Responsible IRB

In accordance with applicable policies of The Pennsylvania State University Institutional Review Board (IRB), the investigator will report, to the IRB, any observed or reported harm (adverse event) experienced by a subject or other individual, which in the opinion of the investigator is determined to be (1) unexpected; and (2) probably related to the research procedures. Harms (adverse events) will be submitted to the IRB in accordance with the IRB policies and procedures.

